**Study Procedures Table – Week 60 to Follow Up**

Assessments	On-treatment Visits										Follow Up o	Telephone Follow-Up p
	Week 60	Week 72	Week 84	Week 96	Week 108	Week 120	Week 132	Week 144	Week 156	ET o		
		Week 168	Week 180	Week 192	Week 204	Week 216	Week 228	Week 240 (EOT)				
Physical Examination	X b	X b	X b	X b	X b	X b	X b	X b	X b	X b	X b	
Vital Signs including Body Weight	X	X	X	X	X	X	X	X	X	X	X	
Waist Circumference		X		X		X		X		X		
Liver Biopsy d								X q		X r		
CP/MELD scores e	X	X	X	X	X	X	X	X	X	X		
Assess Ascites and Hepatic Encephalopathy	X	X	X	X	X	X	X	X	X	X		
Abdominal Ultrasound (OL Phase only)		X		X		X		X		X		
Elastography (if available)				X				X		X		
Health Related Quality of Life Questionnaires g		X		X		X		X		X		
Health Resource Utilization Questionnaires g		X		X		X		X		X		
Stool Frequency Assessment	X	X	X	X	X	X	X	X	X	X	X	
Lifestyle Modification Counseling	X	X	X	X	X	X	X	X	X	X		
Adverse Events	X	X	X	X	X	X	X	X	X	X	X	X
Concomitant Medications	X	X	X	X	X	X	X	X	X	X	X	
Dispense Study Drug	X	X	X	X	X	X	X	X s	X			
Review of Study Drug Dosing Compliance (Pill Count)	X	X	X	X	X	X	X	X	X	X		

Assessments	On-treatment Visits										Follow Up o	Telephone Follow-Up p
	Week 60	Week 72	Week 84	Week 96	Week 108	Week 120	Week 132	Week 144	Week 156	ET o		
		Week 168	Week 180	Week 192	Week 204	Week 216	Week 228	Week 240 (EOT)				
Laboratory Assessments												
Subject Fasting	X	X	X	X	X	X	X	X	X	X	X	
Chemistry i , Hematology, Coagulation	X	X	X	X	X	X	X	X	X	X	X	
Insulin and Lipids		X		X		X		X		X		
HbA1c		X		X		X		X		X		
eGFR	X	X	X	X	X	X	X	X	X	X	X	
Pregnancy Testing j	X	X	X	X	X	X	X	X	X	X	X	
Single PK sampling l	X	X	X	X	X	X	X	X	X	X l		
Blood Collection (Biomarkers)				X				X		X		
Urine Collection				X				X		X		
CCI												
Approximate amount of blood drawn (mL) n	12	15	12	65	12	15	12	65	12	65	10	

- a Subjects starting the OL Phase of the study will complete the same study procedures as during the Randomized Phase of the study, starting with the Day 1 visit
- b Symptom-driven PE
- c CP score to be calculated only at Screening
- d Not to be performed during the OL Phase of the study
- e CCI [REDACTED]
- f CCI [REDACTED]
- g For subjects with questionnaires available at Day 1
- h Adverse Events reporting during Screening is limited to serious adverse events and adverse events related to study procedures
- i Additional testing: digoxin level at Day 1 and Week 1 and as needed in subjects taking digoxin (refer to Section 5.4) and CPK level for subjects in close observation for DILI (refer to Section 7.5)
- j Females of childbearing potential only (refer to Appendix 3). Serum pregnancy test at Screening and urine pregnancy test at Day 1 and every 4 weeks thereafter. Starting at the Week 48 visit, urine pregnancy testing kits will be provided for home testing every 4 weeks, between in-clinic study visits. All females of childbearing potential will be contacted every 4 weeks and asked to report the result of the urine pregnancy tests. FSH testing as per Appendix 3

- k To be performed during the Randomized Phase in all subjects and during the OL Phase, only in subjects with severe hepatic impairment (Child-Pugh Class C) in combination with renal impairment (eGFR < 30 mL/min)
- l To be performed during the OL Phase, only in subjects with severe hepatic impairment (Child-Pugh Class C) in combination with renal impairment (eGFR < 30 mL/min)
- m **CCI**
- n For specific blood volumes at each visit, please refer to the current approved ICF
- o Subjects prematurely discontinuing from the study should complete an ET visit within 30 days of last dose, Follow-Up visit 4 weeks later and a Telephone Follow-Up visit after the ET visit
- p To be performed 12 weeks after the Week 240/EOT or ET visit. At the discretion of the investigator, an unscheduled visit may be completed if the subject reports abnormal or concerning symptoms
- q Not to be performed at the Week 144 visit
- r To be performed at the discretion of the investigator
- s Not to be performed at the Week 240/EOT visits
- t To be collected in all subjects that ET in Randomized or OL Phase

### **Appendix 3. Pregnancy Precautions, Definition for Female of Childbearing Potential, and Contraceptive Requirements**

#### **1) Definitions**

##### **a) Definition of Childbearing Potential**

For the purposes of this study, a female born subject is considered of childbearing potential following the initiation of puberty (Tanner stage 2) until becoming post-menopausal, unless permanently sterile or with medically documented ovarian failure.

Women are considered to be in a postmenopausal state when they are  $\geq 54$  years of age with cessation of previously occurring menses for  $\geq 12$  months without an alternative cause. In addition, women of any age with amenorrhea of  $\geq 12$  months may also be considered postmenopausal if their follicle stimulating hormone (FSH) level is in the postmenopausal range and they are not using hormonal contraception or hormonal replacement therapy.

Permanent sterilization includes hysterectomy, bilateral oophorectomy, or bilateral salpingectomy in a female subject of any age.

##### **b) Definition of Male Fertility**

For the purposes of this study, a male born subject is considered fertile after the initiation of puberty unless permanently sterile by bilateral orchiectomy or medical documentation.

#### **2) Contraception Requirements for Female Subjects**

##### **a) Study Drug Effects on Pregnancy and Hormonal Contraception**

SEL is contraindicated in pregnancy as a malformation effect is suspected, based on non-clinical data. In rats and rabbits, SEL administration was associated with effects on embryo-fetal development at maternally toxic doses.

Preclinical and clinical drug-drug interaction (DDI) data indicate that SEL is unlikely to alter the exposure of hormonal contraceptives through induction of human drug metabolizing enzymes or drug transporters. Please refer to the latest version of the IB for additional information.

## b) Contraception Requirements for Female Subjects of Childbearing Potential

The inclusion of female subjects of childbearing potential requires the use of highly effective contraceptive measures. They must have a negative serum pregnancy test at Screening and a negative pregnancy test on the Day 1 visit prior to randomization. Pregnancy tests will be performed at monthly intervals thereafter. Female subjects must agree to one of the following from Screening until 30 days following the last dose of study drug.

- Complete abstinence from intercourse of reproductive potential. Abstinence is an acceptable method of contraception only when it is in line with the subject's preferred and usual lifestyle.

Or

- Consistent and correct use of 1 of the following methods of birth control listed below
  - Intrauterine device (IUD) with a failure rate of <1% per year
  - Tubal sterilization
  - Essure® micro-insert system (provided confirmation of success 3 months after procedure)\*
  - Vasectomy in the male partner (provided that the partner is the sole sexual partner and had confirmation of surgical success 3 months after procedure)

The above described methods are considered preferred methods of highly effective contraception in this protocol.

- Should female subjects wish to use a hormonally based method, use of a male condom by the female subject's male partner is required. Subjects who utilize a hormonal contraceptive as one of their birth control methods must have used the same method for at least three months prior to study dosing. Hormonally-based contraceptives permitted for use in this protocol are as follows:

Hormonal methods (each method *must* be used with a condom in the male partner):

- Oral contraceptives (either combined or progesterone only)
- Injectable progesterone\*
- Implants of levonorgestrel\*
- Transdermal contraceptive patch\*
- Contraceptive vaginal ring\*

Not all of these methods may be approved in each of the countries where the study is being conducted: please refer to local product information. Additional local regulatory requirements may apply.

\* Not approved in Japan

Female subjects must also refrain from egg donation and in vitro fertilization during treatment and until at least 30 days after the last dose of study drug.

### **3) Contraception Requirements for Male Subjects**

It is theoretically possible that a relevant systemic concentration may be achieved in a female partner from exposure of the male subject's seminal fluid. Therefore, male subjects with female partners of childbearing potential must use condoms during treatment until 30 days after the last dose of study drug. Female partners of male study subjects are asked to select one of the above methods.

### **4) Unacceptable Birth Control Methods**

Birth control methods that are unacceptable include periodic abstinence (e.g., calendar, ovulation, symptothermal, post-ovulation methods), withdrawal (coitus interruptus), spermicides only, and lactational amenorrhea method (LAM). Female condom and male condom should not be used together.

### **5) Procedures to be Followed in the Event of Pregnancy**

Subjects will be instructed to notify the investigator if they become pregnant at any time during the study, or if they become pregnant within 30 days of last study drug dose. Subjects who become pregnant or who suspect that they are pregnant during the study must report the information to the investigator and discontinue study drug immediately. Subjects whose partner has become pregnant or suspects she is pregnant during the study or within 30 days of last study drug must report the information to the investigator. Instructions for reporting pregnancy, partner pregnancy, and pregnancy outcome are outlined in Section [7.6.2.1](#).

**Appendix 4. Common Terminology Criteria for Adverse Events (CTCAE)**

Refer to the Study Reference Binder for additional CTCAE information.

**Appendix 5. West Haven Criteria**

<http://www.mdcalc.com/hepatic-encephalopathy-grades-stages/>

Grade of Hepatic Encephalopathy	Description	Suggested Operative Criteria
Grade I	
 
• Trivial lack of awareness
 
• Euphoria or anxiety
 
• Shortened attention span
 
• Impairment of addition or subtraction
 
• Altered sleep rhythm
 
	Despite oriented in time and space (see below), the patient appears to have some cognitive/ behavioral decay with respect to his or her standard on clinical examination or to the caregivers
Grade II	
 
• Lethargy or apathy
 
• Disorientation for time
 
• Obvious personality change
 
• Inappropriate behavior
 
• Dyspraxia
 
• Asterixis
 
	Disoriented for time (at least three of the followings are wrong: day of the month, day of the week, month, season, or year) ± the other mentioned symptoms
Grade III	
 
• Somnolence to semistupor
 
• Responsive to stimuli
 
• Confused
 
• Gross disorientation
 
• Bizarre behavior
 
	Disoriented also for space (at least three of the following wrongly reported: country, state [or region], city, or place) ± the other mentioned symptoms
Grade IV	
 
• Coma
 
	Does not respond even to painful stimuli

Adapted from {Vilstrup 2014}

Table 3-2.	Analysis Visit Windows for Waist Circumference, Insulin, Homeostasis Model Assessment of Insulin Resistance (HOMA-IR), Lipids and Hemoglobin A1c	24
Table 3-3.	Analysis Visit Windows for ELF test score and components, FibroSure/FibroTest, α_2 -Macroglobin, Haptoglobin, Apolipoprotein A1, C-Reactive Protein (CRP) and Total Bile Acids.....	24
Table 3-4.	Analysis Visit Windows for Elastography and Pooled Cohort Risk and Score.....	25
Table 3-5.	Analysis Visit Windows for Cytokeratin-18 (CK-18) M30 and CK-18 M65	25
Table 3-6.	Analysis Visit Windows for Biopsy Data.....	25
Table 7-1.	Stool Frequency Subscore of Partial Mayo Score	57

LIST OF IN-TEXT FIGURES

Figure 1-1.	Overall Study Design	10
Figure 3-1.	Multiple Testing Flow Chart	17

LIST OF ABBREVIATIONS AND DEFINITION OF TERMS

AE	adverse event
ALP	alkaline phosphatase
ALT	alanine aminotransferase
ANCOVA	analysis of covariance
ARFI	acoustic radiation force impulse
APRI	AST to platelet ratio index
AST	aspartate aminotransferase
α -SMA	α -smooth muscle actin
BLQ	below the limit of quantitation
BMI	body mass index
BP	blood pressure
CI	confidence interval
CLDQ	chronic liver disease questionnaire
CK-18	cytokeratin-18
CMH	Cochran-Mantel-Haenszel
CP	Child-Pugh
CRF	case report form
CRN	clinical research network
CRP	C-reactive protein
CSR	clinical study report
CTCAE	Common Toxicity Criteria for Adverse Events
DILI	drug-induced liver injury
DMC	data monitoring committee
eCRF	electronic case report form
ECG	electrocardiogram
EFS	event-free survival
ELF TM	enhanced liver fibrosis
ET	early termination
EQ-5D	EuroQol five dimensions
FAS	Full Analysis Set
FIB-4	fibrosis-4
Gilead	Gilead Sciences
GGT	gamma glutamyl transferase
HbA1c	Hemoglobin A1c
HCC	hepatocellular carcinoma
HCV	hepatitis C virus
HE	hepatic encephalopathy
Hgb	hemoglobin
HDL	high density lipoprotein

HLGT	high-level group term
HLT	high-level term
HOMA-IR	homeostasis model assessment of insulin resistance
HR	hazard ratio
HRQoL	Health Related Quality of Life
HRUQ	Health Resource Utilization Questionnaires
ID	identification
IFG	impaired fasting glucose
INR	international normalized ratio
ITT	intent to treat
IWRS	interactive web response system
KM	Kaplan-Meier
KMMI	Kaplan-Meier multiple imputation
LDL	low density lipoprotein
LLT	lower-level term
LOCF	last observation carried forward
LOQ	limit of quantitation
MAR	missing at random
MedDRA	Medical Dictionary for Regulatory Activities
MELD	model for end-stage liver disease
MH	Mantel-Haenszel
MI	multiple imputation
MRE	magnetic resonance elastography
NAFLD	non-alcoholic fatty liver disease
NAS	NAFLD activity score
NASH	non-alcoholic steatohepatitis
NFS	NAFLD fibrosis score
NRI	non-responder imputation
OL	open-label
PK	Pharmacokinetic
PIIINP	procollagen III N-terminal propeptide
PT	preferred term
PTM	placebo-to-match
PVE	Pharmacovigilance and Epidemiology
Q1, Q3	first quartile, third quartile
QoL	quality of life
SAE	serious adverse event
SAF	steatosis, activity, and fibrosis
SAP	statistical analysis plan
SD	standard deviation
SEL	selonsertib

SF-36	Short Form (36) Health Survey
SI (units)	international system of units
SWE	shear-wave elastography
SOC	system organ class
SVR	sustained virologic response
TEAE	treatment-emergent adverse event
TFLs	tables, figures, and listings
TIMP1	tissue inhibitor of metalloproteinase
VLDL	very low density lipoprotein
ULN	upper limit of normal
WBC	white blood cell count
WHO	World Health Organization
WPAI	work productivity and activity impairment questionnaire

1. INTRODUCTION

This statistical analysis plan (SAP) describes the statistical analysis methods and data presentations to be used in tables, figures and listings (TFLs) for the interim analysis at Week 48 and final analysis at Week 240 for Study GS-US-384-1943.

This analysis plan is based on the study protocol Amendment 2 dated 31 May 2018 and the electronic case report form (eCRF). The SAP will be finalized before breaking the blind for the interim analysis. Any changes made after the finalization of the SAP will be documented in the clinical study report (CSR).

1.1. Study Objectives

The primary objective of this study is as follows:

- To evaluate whether selonsertib (SEL) can cause fibrosis regression and reduce progression to cirrhosis and associated complications in subjects with NASH and bridging (F3) fibrosis

The secondary objective of this study is as follows:

- To assess the safety and tolerability of SEL in subjects with NASH and bridging (F3) fibrosis

The exploratory objectives of this study are as follows:

[figure not shown]

1.2. Study Design

This is a Phase 3, randomized, double-blind, placebo-controlled study evaluating the safety and efficacy of SEL in subjects with NASH and bridging (F3) fibrosis.

The overall study design is presented graphically in [Figure 1-1](#).

Figure 1-1. Overall Study Design

- EOT = end of treatment; ET = early termination; PTM = Placebo-to-Match

Subjects meeting the study’s entry criteria were randomly assigned in a 2:2:1 ratio to 1 of 3 treatment groups: Group A, Group B and Group C, respectively, as shown in [Figure 1-1](#). Randomization was stratified by the presence or absence of diabetes mellitus (determined by medical history or based on Screening laboratory values if previously undiagnosed [ie, hemoglobin A1c (HbA1c) \geq 6.5% or fasting plasma glucose \geq 126 mg/dL]) and by Enhanced Liver Fibrosis (ELF™) test score \geq 9.76 or $<$ 9.76 during Screening. Study drugs will be administered for up to a total of 240 weeks.

Subjects who experience a clinical event (except all-cause mortality and liver transplantation) prior to completing the Week 240 Visit of the Randomized Phase will be offered the option to rollover into an Open-Label (OL) Phase for a total treatment duration of 240 weeks inclusive of the Randomized Phase. Rollover into the OL Phase of the study must occur within 60 days of confirmation of the event. Subjects starting the OL Phase of the study will complete the same study procedures as during the Randomized Phase of the study, **CCI**

The schedule of assessments is provided as an appendix to this analysis plan ([Appendix 1](#)).

1.3. Sample Size and Power

With a sample size of 320 subjects in each active treatment arm and 160 subjects in the placebo arm, the study has 94% power to detect a difference in the proportion of subjects with a ≥ 1 -stage improvement in fibrosis without worsening of NASH of 15% or more at Week 48 at a significance level of 0.025 (2-sided), assuming the proportion of subjects that meet the endpoint in the placebo arm is 12%.

With regard to the clinical efficacy endpoint, subjects will be followed for a period of up to 240 weeks. The estimate of the expected event rate is 30% in untreated patients, producing an expected EFS rate of 70% at 240 weeks in the placebo arm. SEL is expected to improve the EFS rate to 83.7% (expected event rate of 16.3%) compared with placebo (hazard ratio (HR), 0.50). We also expect a 20% overall dropout rate. Given the above assumptions, for comparison of the SEL arms versus the placebo arm, together with a total sample size of 800 subjects (2:2:1 ratio), and assuming the log-rank test statistic is evaluated using a 2-sided 0.025 significance level, the study will have 85% power to evaluate the superiority of each SEL arm versus placebo with respect to EFS.

Therefore, the overall power for the trial, assuming independence between the primary efficacy endpoint and clinical efficacy endpoint, is 80% ($94\% \times 85\%$). It should be noted that this is a lower bound estimate as these 2 endpoints are expected to be positively correlated.

2. TYPE OF PLANNED ANALYSIS

2.1. DMC Interim Analyses

An external Data Monitoring Committee (DMC) that consists of 3 hepatologists and a PhD statistician will review the progress of the study, perform interim reviews of safety data, and provide recommendations to Gilead whether the nature, frequency, and severity of adverse events (AEs) associated with study treatment warrant the early termination of the study in the best interests of the participants, whether the study should continue as planned, or whether the study should continue with modifications.

The initial meeting of the DMC will occur after 50 subjects have completed their Week 4 visit and approximately every 6 months thereafter to monitor the study for safety events.

The DMC's specific activities will be defined by a mutually agreed upon charter, which will define the DMC's membership, conduct, and meeting schedule.

While the DMC will be asked to advise Gilead regarding future conduct of the study, including possible early study termination, Gilead retains final decision-making authority on all aspects of the study.

2.2. Interim (Week 48) Analysis

When all subjects have completed the Randomized Phase Week 48 visit, or have a clinical event before Randomized Phase Week 48 visit, or have prematurely discontinued from the study, superiority of each SEL arm relative to the placebo arm will be assessed with respect to the primary histology efficacy endpoint.

2.3. Final (Week 240) Analysis

After all subjects have completed the study, or have prematurely discontinued from the study, outstanding data queries have been resolved or adjudicated as unresolvable, and the data have been cleaned and finalized, the study blind will be broken and the final analysis of the data will be performed. The final analysis will assess the superiority of each SEL arm relative to placebo with respect to the primary clinical efficacy endpoint of EFS.

3. GENERAL CONSIDERATIONS FOR DATA ANALYSES

Analysis results will be presented using descriptive statistics. For categorical variables, the number and percentage of subjects in each category will be presented; for continuous variables, the number of subjects (n), mean, standard deviation (SD), median, first quartile (Q1), third quartile (Q3), minimum, and maximum will be presented.

By-subject listings will be presented for all subjects in the All Randomized Analysis Set and sorted by subject identification (ID) number, visit date, and time (if applicable). Data collected on log forms, such as AEs, will be presented in chronological order within subject. The treatment group to which subjects were initially assigned will be used in the listings. Age, sex at birth, race, and ethnicity will be included in the listings, as space permits.

3.1. Analysis Sets

Analysis sets define the subjects to be included in an analysis. Analysis sets and their definitions are provided in this section. Subjects included in each analysis set will be determined before the study blind is broken for analysis. The analysis set will be identified and included as a subtitle of each table, figure, and listing. Subjects who have been randomized but never dosed will also be summarized.

A listing of reasons for exclusion from analysis sets will be provided by subject.

3.1.1. All Randomized Analysis Set

All Randomized Analysis Set includes all subjects who were randomized in the study.

3.1.2. Full Analysis Set

The Full Analysis Set (FAS) includes all subjects who were randomized in the study and received at least 1 dose of study drug. This is the primary analysis set for efficacy analyses.

3.1.3. Safety Analysis Set

The Safety Analysis Set includes all subjects who took at least 1 dose of study drug. This is the primary analysis set for safety analyses.

Safety analysis set for the OL Phase (OL Safety Analysis Set) includes all subjects who were enrolled into the OL Phase and received at least 1 dose of OL study drug. This is the primary analysis set for OL Phase safety analyses.

3.1.4. Pharmacokinetic Analysis Set

The PK Analysis Set will include all randomized subjects who took at least 1 dose of study drug and had at least 1 nonmissing postdose concentration of SEL (and/or its metabolite GS-607509) reported by the bioanalytical laboratory. This is the primary analysis set for all PK analyses.

3.2. Subject Grouping

For analyses based on the FAS, subjects will be grouped according to the treatment to which they were randomized. For analyses based on the Safety Analysis Set, subjects will be grouped according to actual treatment received. The actual treatment received will differ from the randomized treatment only when the actual treatment differs from the randomized treatment for the entire treatment duration. In this case, the actual treatment received is defined as the treatment received for the entire treatment duration.

For safety analyses, subjects will be grouped into the following:

Randomized Phase (only Randomized Phase data will be summarized for these groups)

- 1) SEL 18 mg: This group includes all subjects who received SEL 18 mg in the Randomized Phase.
- 2) SEL 6 mg: This group includes all subjects who received SEL 6 mg in the Randomized Phase.
- 3) SEL Pooled: This group includes all subjects who received SEL 18 mg or SEL 6 mg in the Randomized Phase.
- 4) Placebo: This group includes all subjects who received only placebo in the Randomized Phase.

Open-Label Phase (only OL Phase data will be summarized for this group):

OL SEL 18 mg: This group includes all subjects who received OL study drug.

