## 1.5. Risk/Benefit Assessment for the Study

This study will provide information regarding the safety and efficacy of SEL for the treatment of patients with bridging fibrosis due to NASH. The potential benefits of SEL for the treatment of NASH were shown in the Phase 2 study GS-US-384-1497. As described above, rapid fibrosis regression was observed in a greater proportion of SEL-treated versus SIM-treated subjects after only 24 weeks of treatment. Although this study did not include a placebo control arm, these response rates to SEL are substantially higher than reported in the placebo groups of Phase 2 trials for other compounds in development for NASH {[Neuschwander-Tetri 2015](#), [Ratziu 2016](#)}. In addition, reductions in liver biochemistries (e.g., ALT, aspartate aminotransferase [AST], gamma glutamyl transferase [GGT], liver fat content by magnetic resonance imaging-proton density fat fraction [MRI-PDFF], lobular inflammation, liver stiffness by magnetic resonance elastography [MRE], and biomarkers of apoptosis and necrosis (serum CK-18 M30 and M65 levels) were observed, particularly in fibrosis responders.

Subjects randomized to the placebo control arm in the study may benefit from frequent medical monitoring and close assessment of their NASH and associated pathologies during the duration of placebo treatment. For example, the identification of progression to cirrhosis during this trial will trigger close monitoring for complications of cirrhosis (e.g., esophageal varices and HCC) that may not otherwise be performed. Moreover, all subjects, including those treated with placebo during the Randomized Phase, have the opportunity to receive SEL treatment during the Open-Label Phase in the event of progression to cirrhosis.

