### 6.7. Open-Label Phase

Subjects who progress to cirrhosis on liver biopsy or experience a hepatic clinical event (refer to Section 3.2) prior to completing the Week 240 Visit of the Randomized Phase will be offered the option to rollover into an Open-Label (OL) Phase of the study. Each of the clinical events (except death and liver transplantation) will require confirmation by a Hepatic Events Adjudication Committee. All deaths will be reviewed by this committee to determine if they are liver-related.

Subjects who undergo liver transplantation are not eligible to participate in the OL Phase of the study and should discontinue from the study immediately. Subjects who have permanently discontinued study drugs are not eligible for the OL Phase of the study.

Once a clinical event (except histological progression to cirrhosis, death and liver transplantation) is confirmed by the Hepatic Events Adjudication Committee, the subject will no longer participate in the Randomized Phase and will be offered the option to receive SEL 18 mg in the OL Phase for a total treatment duration of 240 weeks inclusive of the Randomized Phase.

Rollover into the OL Phase of the study must occur within 60 days of confirmation of the event. Subjects starting the OL Phase of the study will complete the same study procedures as during the Randomized Phase of the study, CCI

. Hepatic clinical events will be adjudicated and deaths will be reviewed by the Hepatic Events/DILI Adjudication Committee only during the Randomized Phase of the study; potential DILI events and cardiovascular events including deaths will continue to be adjudicated in the OL Phase by the Hepatic Events/DILI Adjudication Committee and the Cardiovascular Events Adjudication Committee, respectively.

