### 8.8. Safety Analysis

Safety will be assessed during the study through the reporting of AEs, and by clinical laboratory tests and vital sign assessments at various time points during the study. Concomitant medication usage will also be assessed throughout the study.

All safety data collected on or after the date that SEL or PTM SEL was first dispensed up to the date of last dose of SEL or PTM SEL plus 30 days will be summarized by treatment group, including extent of exposure, adverse events, laboratory evaluations, and immunogenicity.

Safety data from the OL Phase will be summarized for overall subjects who roll-over into the OL Phase for safety review.

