7.1.6. Summaries of Adverse Events and Deaths

Treatment-emergent adverse events and AEs > 30 days posttreatment will be summarized for the Safety Analysis Set/OL Safety Analysis Set according to the subject grouping defined in Section 3.2.

The number and percentage of subjects who experienced at least 1 TEAE will be provided and summarized by SOC, HLT and PT. For other AEs described below, summaries will be provided by SOC and PT:

- TEAEs by severity grade
- TEAEs of Grade 3 or higher (by maximum severity)
- TEAEs of Grade 2 or higher
- All TE treatment-related AEs
- TE Treatment-related AEs of Grade 3 or higher (by maximum severity)

- TE Treatment-related AEs of Grade 2 or higher
- All TE SAEs
- All TE treatment-related SAEs
- All TE treatment-related AEs by severity grade
- Death
- All TEAEs leading to discontinuation of study drug In the Randomized Phase, TEAEs leading to discontinuation of study drug include 2 categories: protocol-specified clinical events, and TEAEs leading to premature discontinuation of study drug. The latter will be provided in a separate summary table.

A brief, high-level summary of AEs described above (except for the summary by severity grade) will be provided by treatment group and by the number and percentage of subjects who experienced the above AEs. All deaths observed in the study and subjects who completed randomized study drug due to protocol-specified clinical events will be also included in this summary.

Multiple events will be counted only once per subject in each summary. Adverse events will be summarized and listed first in alphabetic order of SOC and HLT within SOC (if applicable), and then in descending order of PTs by frequency in the (OL) SEL 18 mg group within each SOC or HLT in the Randomized/OL Phase. For summaries by severity grade, the most severe grade will be used for those AEs that occurred more than once in an individual subject in the Randomized/OL Phase.

In addition to the above summary tables, the following tables will be summarized by PT only, in descending order of frequency in the (OL) SEL 18 mg group for the Randomized/OL Phase:

- All TEAEs
- TEAEs of Grade 3 or higher (by maximum severity)
- TEAEs of Grade 2 or higher
- TE treatment-related AEs
- TE Treatment-related AEs of Grade 3 or higher (by maximum severity)
- TE Treatment-related AEs of Grade 2 or higher
- All TESAEs
- All TE treatment-related SAEs

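### Open-Label safety is tabulated in one pooled SEL 18 mg column, which hides first-exposure rates after a hepatic event; columns by randomised arm should be added

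*SAP*

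**What the plan says.** - **Grouping.** SAP 3.2 defines four groups for Randomized Phase safety but only one for the OL Phase: "OL SEL 18 mg: This group includes all subjects who received OL study drug". Protocol 8.8 agrees: "Safety data from the OL Phase will be summarized for overall subjects who roll-over into the OL Phase for safety review".
- **Where it applies.** SAP Section 7 uses the 3.2 grouping for all safety analyses. SAP 7.1.6 repeats this for adverse events, which "will be summarized for the Safety Analysis Set/OL Safety Analysis Set according to the subject grouping defined in Section 3.2". SAP 4.2.1 uses it for exposure. SAP 7.1.7.1 and 7.2.4 summarise cardiovascular and DILI events by treatment group in the OL Phase, where 3.2 supplies only one group.
- **Who enters.** Protocol 1.5 states that "all subjects, including those treated with placebo during the Randomized Phase, have the opportunity to receive SEL treatment during the Open-Label Phase". Under Protocol 6.7, subjects with a qualifying event "will be offered the option to receive SEL 18 mg in the OL Phase for a total treatment duration of 240 weeks". The same section sets a limit: "Subjects who have permanently discontinued study drugs are not eligible for the OL Phase of the study".
- **Restart.** SAP 7.1.5.1 defines treatment-emergent events separately for each phase, mainly by onset date. SAP 7.2.2.1 grades laboratory changes against the baseline of the corresponding phase. SAP 3.8.3 takes the OL liver-test baseline as the average from OL Day -55 to OL Day 1.
- **Where the randomised arm survives.** Listings show the arm first assigned (SAP Section 3). The final disposition summary is by treatment group and includes OL drug completion and reasons for stopping (SAP 4.1).

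**The concern.** Three exposure histories share one denominator: first exposure, a step from 6 mg to 18 mg, and continuation at 18 mg. The plan's own rules make them unlike each other. Prior SEL users are selected for not having permanently stopped drug. An event that began on randomised SEL and persists will generally not count as OL treatment-emergent. Prior users may also bring on-drug laboratory values into the OL baseline, whereas ex-placebo subjects bring a SEL-free one.

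No OL adverse-event or laboratory rate by prior treatment is planned anywhere. Entry to the trial requires F3 fibrosis and no prior decompensation (Protocol 4.2 and 4.3), so the OL Phase is where, within this trial, subjects first start SEL after progressing to cirrhosis or having a hepatic event. A reader of the OL tables could not see what happened to them.

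**Working it through.** The documents give no planned size or precision for OL safety, so there is no stated figure to reproduce. The event rates used below are internally consistent: 0.70^0.50 = 0.837, which matches the stated EFS of 83.7% at a hazard ratio of 0.50.

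**Inputs**
- Arm sizes: 320, 320 and 160 (SAP 1.3).
- EFS event rates over 240 weeks: 30% on placebo and 16.3% on SEL (SAP 1.3).
- Phase 2 diarrhoea: 66/565 = 11.7% on SEL against 13/184 = 7.1% on placebo or simtuzumab (Protocol 1.5).
- Phase 2 liver-test elevations: 17/564 = 3.0% on SEL against 4/182 = 2.2% on placebo (Protocol 1.5).
- Assumption: the same fraction of events rolls over in each arm.

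**Step 1: ex-placebo share, w**

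Upper bound on entrants per arm = arm size × event rate.

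| Scenario | Ex-placebo | Ex-6 mg | Ex-18 mg | Total | w |
|---|---|---|---|---|---|
| HR 0.50 in both arms | 0.30 × 160 = 48 | 0.163 × 320 = 52.2 | 52.2 | 152.3 | 31.5% |
| HR 0.50 in the 18 mg arm only | 48 | 0.30 × 320 = 96 | 52.2 | 196.2 | 24.5% |
| No EFS effect | 48 | 96 | 96 | 240 | 20.0% |

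Cutting each count by the planned 20% dropout gives about 38, 42 and 42 in the first row. The share does not change.

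**Step 2: what the pooled column shows**

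Pooled rate = w × r(new) + (1 − w) × r(prior). The excess shown over the prior-user rate is w × [r(new) − r(prior)]. An excess confined to first exposure is therefore multiplied by 0.20 to 0.315.

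**Step 3: illustration with the protocol's own rates**

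This assumes that new users run at the Phase 2 SEL rate and all prior users at the control rate.
- Diarrhoea: the excess is 11.7 − 7.1 = 4.6 points. It appears as 0.20 × 4.6 = 0.9 points (pooled 8.0%) to 0.315 × 4.6 = 1.5 points (pooled 8.5%).
- Liver-test elevations, at w = 31.5%: 0.315 × 3.0 + 0.685 × 2.2 = 2.5%. The excess of 0.8 points appears as about 0.3.

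**Step 4: if ex-6 mg subjects respond like new users of 18 mg**

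The share new to 18 mg is (48 + 52.2)/152.3 = 65.8% at HR 0.50 in both arms, and (48 + 96)/240 = 60% with no effect. The pooled column would then show roughly three fifths to two thirds of the excess. The documents do not say which assumption is closer, and a pooled column cannot show it.

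**The case against.** The strongest reply is that little rests on these tables. First exposure is assessed by dose against concurrent placebo in the Randomized Phase (planned 640 SEL and 160 placebo), and the companion trial covers compensated cirrhosis (Protocol 1.2.11). The OL Phase is descriptive and uncontrolled. Its entrants are selected by a post-randomisation event, so even an ex-placebo column could not separate drug harm from advancing disease. DILI and cardiovascular events stay under adjudication in the OL Phase, a DMC meets about every six months, and the SAP follows the protocol. All of this stands. It limits the point to first exposure after a hepatic event or progression to cirrhosis in this trial, but it does not give a rate for those subjects.

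A reader might go further and infer four things that the documents do not support:
- *The pooled table shows less than half of the true new-user rate.* That needs a near-zero rate in prior users. With the protocol's control rates, pooled diarrhoea at w = 31.5% is 8.5/11.7 = 73% of the new-user rate. It is the excess that shrinks to a third or less, not the rate.
- *Most OL subjects have already passed the early risk of 18 mg.* At HR 0.50 only 52 of 152 (34%) were already on 18 mg.
- *Only the listings keep the randomised arm.* The final disposition summary keeps it too, although it gives counts and reasons for stopping, not adverse-event or laboratory rates.
- *About 152 subjects will enter.* That is a ceiling. Deaths and transplants do not roll over, F4 found at the Week 240 biopsy comes too late, and rollover is optional.

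**Conclusion.** The point holds as a limited weakness of presentation. The single OL group gives a rate that describes neither starting nor continuing SEL. Ex-placebo subjects make up about 20% to 32% of it, so about one fifth to one third of an excess confined to first exposure would show. This rests on the plan's event rates, equal rollover uptake across arms, and ex-6 mg subjects behaving like other prior users; the visible share is larger if they react to the step to 18 mg. The Phase 2 rates illustrate the arithmetic and do not predict OL results. The grouping does not contradict the protocol, does not affect any efficacy inference, and does not weaken the controlled comparison of first exposure in the Randomized Phase.

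**What to change.** In SAP 3.2, keep the pooled OL SEL 18 mg column as a total and add three columns by randomised arm: placebo to 18 mg, 6 mg to 18 mg, and 18 mg to 18 mg. Use them for the OL summaries of exposure, treatment-emergent and serious adverse events, graded laboratory abnormalities, liver-test criteria (SAP 7.2.3), DILI and cardiovascular events. Show counts with percentages. Protocol 8.8 can stay as it is, since the overall summary remains.

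The cost is SAP wording and table programming. Randomised arm is already held for every OL subject, and no procedure or treatment changes. The drawback is small cells: at most about 50 subjects per column at HR 0.50, and probably fewer. The columns should be read descriptively, without comparison between them.
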